- If an investigator, site personnel performing assessments, or patient is unblinded;
- If the investigator or sponsor decides that the patient should be withdrawn from study drug; if the investigator decides to permanently discontinue study treatment because of an SAE or a clinically significant laboratory value, Lilly or its designee should be alerted immediately.
- if the patient or the patient's designee, for example, legal guardian, requests that the patient be withdrawn from study drug

Patients who stop the study drug permanently will receive another glucose-lowering intervention (Section 7.7.1) and will continue participating in the trial according to the protocol to collect all planned efficacy and safety measurements.

Patients discontinuing from the investigational product prematurely for any reason should complete AE and other follow-up procedures per Section 2 Schedule of Activities, Section 9.2 Adverse Event, and Section 9.4 Safety of this protocol.

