9.2.2.1. Hypoglycemia

Patients will collect information on episodes of hypoglycemia starting from Visit 2 until the last study visit (ET visit or 801). Patients will be trained about signs and symptoms of hypoglycemia, how to treat hypoglycemia, and how to collect appropriate information for each episode of hypoglycemia in the study according to the Schedule of Activities (Section 2). Site personnel will enter this information into the hypoglycemia eCRF at each visit.

Investigators should use the following definitions and criteria when diagnosing and categorizing an episode considered to be related to hypoglycemia (the BG values in this section refer to values determined by a laboratory or International Federation of Clinical Chemistry and Laboratory Medicine plasma-equivalent glucose meters and strips) in accordance with the 2020 ADA position statement on glycemic targets:

Level 1 hypoglycemia:

Glucose <70 mg/dL (3.9 mmol/L) and \geq 54 mg/dL (3.0 mmol/L): Level 1 hypoglycemia can alert a person to take action such as treatment with fast-acting carbohydrates. Providers should continue to counsel participants to treat hypoglycemia at this glucose alert value.

Level 2 hypoglycemia:

Glucose <54 mg/dL (3.0 mmol/L): This is also referred to as documented or blood glucose confirmed hypoglycemia with glucose <54 mg/dL (3.0 mmol/L). This glucose threshold is clinically relevant regardless of the presence of absence of symptoms of hypoglycemia.

Level 3 hypoglycemia:

Severe hypoglycemia (in adults): A severe event characterized by altered mental and/or physical status requiring assistance for treatment of hypoglycemia. For example, participants had altered mental status, and could not assist in their own care, or were semiconscious or unconscious, or experienced coma with or without seizures, and the assistance of another person was needed to actively administer carbohydrate, glucagon, or other resuscitative actions. Glucose measurements may not be available during such an event, but neurological recovery attributable to the restoration of glucose concentration to normal is considered sufficient evidence that the event was induced by a low glucose concentration.

- The determination of a hypoglycemic event as an episode of severe hypoglycemia, as defined above, is made by the investigator based on the medical need of the participant to have required assistance and is not predicated on the report of a participant simply having received assistance.

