10.3. Statistical Analyses

10.3.1. General Statistical Considerations

Statistical analysis of this study will be the responsibility of Lilly or its designee. Any change to the data analysis methods described in the protocol will require an amendment ONLY if it changes a principal feature of the protocol. Any other change to the data analysis methods described in the protocol, and the justification for making the change, will be described in the statistical analysis plan (SAP) or the clinical study report (CSR). Additional exploratory analyses of the data will be conducted as deemed appropriate.

Unless otherwise specified, listings will include all randomized patients. Both efficacy and safety analyses will be conducted using the intention to treat (ITT) population. Unless otherwise

specified, efficacy data from patients who started rescue therapy or discontinued study treatment prematurely will be censored from the point of initiating rescue treatment or premature discontinuation onwards. Selected analyses will also be conducted using the PP and Completers populations. The PP and Completers populations are subsets of the ITT population.

Unless otherwise noted, all tests of treatment effects will be conducted at a 2-sided alpha level of 0.05, and CIs will be calculated at 95%, 2-sided. All tests of interactions between treatment groups and other factors will be conducted at a 2-sided alpha level of 0.10.

The baseline will be at the randomization visit (Visit 3). If baseline data are missing, the last nonmissing measurement taken prior to Visit 3 will be used.

The primary and key secondary continuous efficacy measures will be analyzed with mixed-model repeated measures (MMRM) using restricted maximum likelihood (REML) (Section 10.3.3.1). The model will include factors for treatment, OAM usage (metformin alone, acarbose alone, metformin and acarbose), visit, and treatment-by-visit as fixed effects, baseline as a covariate, and patient as random effect. An unstructured covariance structure will be used to model the within-patient variability. If this model fails to converge, the following covariance structures will be tested in order:

- Toeplitz with heterogeneity
- Autoregressive with heterogeneity, by visit
- Compound symmetry with heterogeneous variances, by visit
- Toeplitz
- Autoregressive
- Compound symmetry without heterogeneous variances, by visit

The first covariance structure that converges will be used.

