10.3.4.3. Hypoglycemic Episodes

Section 9.2.2.1 contains definitions of categories of hypoglycemia. A listing of individual hypoglycemic episodes by patient will be presented. Summary reports will include both incidence and rates of hypoglycemia for the ITT population (with post-rescue data censored). Categories of hypoglycemia for analysis include "documented", "documented symptomatic", "severe hypoglycemia", and "nocturnal".

Hypoglycemic episodes will be analyzed using 2 hypoglycemic thresholds: Level 1 (glucose alert level, <3.9 mmol/L [70 mg/dL] and ≥3.0 mmol/L [54 mg/dL]) and Level 2 (clinically significant hypoglycemia level, <3.0 mmol/L [54 mg/dL]). Other categories, including the categories above defined with different glucose thresholds, may also be included in these analyses when deemed appropriate.

The incidence of hypoglycemic episodes will be summarized by frequencies and proportion for each treatment group, by visit as well as overall. Treatment differences in the incidence of hypoglycemic episodes will be assessed using Fisher's exact tests. Treatment differences in rates of hypoglycemic episodes (episodes/patient/30 days; episodes/patient/year) will be analyzed using a generalized linear mixed-effects model assuming negative binomial distribution. The model will include treatment, OAM usage (metformin alone, acarbose alone, metformin and acarbose), baseline HbA1c stratum ($<8.5\%$ vs. $\geq8.5\%$), visit, treatment-by-visit interaction, and baseline hypoglycemia rate. The logarithm of days between visits will be included as an offset to account for possible unequal duration between visits and between patients.

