- Removed analyses for hypoglycemia events with post-rescue or early-discontinuation data.
- Removed interaction term and covariate in negative binomial model for hypoglycemia events.
- Modified shift tables for selected analytes.
- Added baseline insulin dose in subgroup analysis.
- Updated number of patients required for subgroup analysis.
- Added Chinses EQ-5D-5L score in addition to UK score.

4. Study Objectives

Table 4.1 Table 4.1 Objectives and Endpoints presents the objectives and endpoints of the study.

Table 4.1 Objectives and Endpoints

Objectives	Endpoints

Primary
 
 To show the superiority of the addition of dulaglutide 1.5 mg QW compared to the addition of once weekly placebo to titrated insulin glargine, with metformin and/or acarbose, on change from baseline in HbA1c after 28 weeks of treatment in adult Chinese patients with T2D. 	
 The change in HbA1c from baseline to Week 28.

Key Secondary (controlled for Type I error)
 
Efficacy:
 
 To compare the addition of dulaglutide 1.5 mg QW with the addition of placebo QW to titrated basal insulin glargine for other parameters of glucose control and body weight change after 28 weeks of treatment in patients with T2D. 	
 Proportion of patients achieving HbA1c target of <7.0%. Change from baseline in body weight. Change from baseline in FSG (central lab).

Additional Secondary
 
Efficacy:
 
 To compare the addition of dulaglutide 1.5 mg QW with the addition of placebo QW to titrated basal insulin glargine for the following parameters after 28 weeks of treatment in patients with T2D. 	
 Proportion of patients achieving HbA1c target of ≤6.5%. Proportion of patients achieving HbA1c target of <7.0% and with no weight gain (<0.1 kg) at 28 weeks, and without documented symptomatic hypoglycemia (BG <3.0 mmol/L) during the maintenance period (Weeks 12-28). Proportion of patients achieving HbA1c target of <7.0% at 28 weeks, and without documented symptomatic hypoglycemia (BG <3.0 mmol/L) during the maintenance period (Weeks 12-28). Proportion of patients achieving HbA1c target of <7.0%, and without weight gain (<0.1 kg) at 28 weeks. Changes from baseline in BG from daily SMBG profiles. Changes from baseline in daily mean insulin glargine doses.

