5.2. General Considerations

This plan describes all priori statistical analyses for efficacy and safety that will be performed.

Statistical analysis of this study will be the responsibility of Eli Lilly and Company (Lilly), although implementation of the statistical analysis may be delegated to a third party. Any change to the data analysis methods described in the protocol will require an amendment ONLY if it changes a principal feature of the protocol. Any other change to the data analysis methods described in the protocol, and the justification for making the change, will be described in this SAP and/or in the clinical study report (CSR). Additional exploratory analyses of the data will be conducted, as deemed appropriate.

All analyses will be implemented using Version 9.4 SAS or higher.

Unless otherwise specified, listings will include all randomized patients. Both efficacy and safety analyses will be conducted using the intent-to-treat (ITT) population. Unless otherwise specified, efficacy data from patients who started rescue therapy or premature treatment discontinuation (whichever occurs first) will be censored from the point of initiating rescue treatments or early discontinuation onwards. Safety analysis will not censor this part of data. Selected analyses will also be conducted using the per-protocol (PP) and Completers populations. The PP and Completers populations are subsets of the ITT population.

Unless otherwise noted, all tests of treatment effects will be conducted at a 2-sided alpha level of 0.05, and confidence intervals (CIs) will be calculated at 95%, 2-sided. All tests of interactions between treatment groups and other factors will be conducted at a 2-sided alpha level of 0.10.

The baseline data will be collected at Visit 3. For all variables, including HbA1c, if baseline data are missing, the last non-missing measurement taken prior to this visit will be used for the baseline measurement.

Patients will be randomized in a 1:1 ratio to (1) dulaglutide 1.5 mg QW add-on to insulin glargine or (2) placebo QW add-on to insulin glargine, with metformin and/or acarbose. Patients will also be stratified by HbA1c at Visit 1 (screening) (<8.5% vs. \geq 8.5%) and OAM usage (metformin alone, acarbose alone, metformin and acarbose) at Visit 3 (randomization) to achieve

between-group comparability and to mitigate against confounding the effects of the treatments with severity of disease or treatment with metformin and/or acarbose.

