5.11.2. Hypoglycemic Episodes

Level 1, 2, 3, and nocturnal hypoglycemia will be included for summary and analysis.

Classification of these hypoglycemic events are shown in [Table 5.2](#).

Table 5.2 Definitions of Hypoglycemic Event Categories

Glycemic criteria/description	
Level 1 (Glucose Alert Value)	Blood Glucose <70 mg/dL (3.9 mmol/L) and >= 54 mg/dL (3.0 mmol/L)
Level 2 (Clinically Significant Hypoglycemia)	Glucose <54 mg/dL (3.0 mmol/L)
Level 3 (Severe Hypoglycemia)	A severe event characterized by altered mental and/or physical status requiring assistance for recovery (no specific glucose threshold).

Nocturnal hypoglycemia: a hypoglycemia event (including severe hypoglycemia) that occurs between bedtime and waking.

A listing of the individual hypoglycemic episodes will be presented using all randomized population. Summary reports will include both incidence and rates of hypoglycemia for each visit including safety follow-up, as well as in stabilization period (Week 0 – 4), maintenance period (Week 12 – 28) and overall period (Week 0 – 28) will be reported for the ITT population without post-rescue or early-discontinuation data.

The incidence of hypoglycemic episodes will be summarized by frequencies and proportion for each treatment group using ITT population, by visit, stabilization period, maintenance period as well as overall period. The overall frequency and proportion are calculated as the total number of patients and proportion of patients reporting hypoglycemic episodes through safety follow-up. The maintenance frequency and proportion are calculated as the total number of patients and

proportion of patients reporting hypoglycemic episodes during Weeks 12 to 28. Treatment differences in the incidence of hypoglycemic episodes will be assessed using Fisher's exact test.

The rates of hypoglycemic episodes (episodes/patient/year) for each visit, overall and maintenance period will be analyzed using a generalized linear mixed-effects model assuming negative binomial distribution. The model will include treatment, OAM usage (metformin alone, acarbose alone, metformin and acarbose), baseline HbA1c strata (<8.5% vs. $\geq 8.5\%$), as fixed effects. The logarithm of days between visits will be included as an offset to account for possible unequal duration between visits and between patients.

Three additional categories of hypoglycemia will be used in efficacy analysis in Section 5.8.1 and 5.9.2. The definitions are below:

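### SAP 5.11.2 drops hypoglycaemia after rescue or early drug stop, against SAP 5.2 and beyond protocol 10.3.4.3, and leaves no uncensored between-arm comparison by level

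*SAP*

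**What the plan says.** Four places set the data rule for this endpoint.

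- SAP 5.2 censors efficacy data from rescue or early treatment discontinuation, then adds: "Safety analysis will not censor this part of data". The sentence carries no exception.
- Protocol 10.3.1 likewise confines censoring after an early stop to efficacy: "efficacy data from patients who started rescue therapy or discontinued study treatment prematurely will be censored".
- Protocol 10.3.4.3 has its own rule for hypoglycaemia, which mentions rescue but not early stop: "Summary reports will include both incidence and rates of hypoglycemia for the ITT population (with post-rescue data censored").
- SAP 5.11.2 excludes both kinds of data: incidence and rates "will be reported for the ITT population without post-rescue or early-discontinuation data".

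The SAP revision history (Section 3) lists the change among the key changes in version 2.0: "Removed analyses for hypoglycemia events with post-rescue or early-discontinuation data". It places that version before first unblinding and gives no reason for the removal.

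The excluded data will exist. Protocol 8.1.1 says of patients who stop study drug that they "will continue participating in the trial according to the protocol to collect all planned efficacy and safety measurements". Protocol 9.2.2.1 runs hypoglycaemia collection from Visit 2 to the last study visit.

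SAP 5.11.2 compares incidence by Fisher's exact test. It analyses rates by a negative binomial model whose offset is the log of the number of days separating visits.

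**The concern.** One named safety endpoint has three incompatible data rules, and the narrowest governs the only between-arm analyses by level. Fisher's test takes no account of time at risk. A patient cut at Week 8 stays in the ITT denominator but can contribute an event only in those eight weeks. If the arms lose different amounts of time, counted incidence differs between them even when true risk does not.

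Off-drug time is also handled unevenly. SAP 5.11.2 counts overall incidence through safety follow-up, when completers no longer receive study drug, yet it discards the off-drug weeks of early stoppers. A consistent on-treatment rationale would not do both. The same section also defines the overall period as Weeks 0 to 28, which conflicts with counting through follow-up.

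At stake is the hypoglycaemia comparison. Protocol 5.4 cites the absence of added hypoglycaemia risk in the earlier dulaglutide and glargine trial as part of the rationale, and SAP Table 4.1 sets the safety objective through 32 weeks.

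**Working it through.** **Side-by-side reading**

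| Source | After rescue | After early drug stop |
|---|---|---|
| SAP 5.2 (all safety) | keep | keep |
| Protocol 10.3.4.3 (hypoglycaemia) | censor | not mentioned |
| Protocol 10.3.1 | censor efficacy only | censor efficacy only |
| SAP 5.11.2 (hypoglycaemia) | drop | drop |

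The SAP contradicts itself in both columns. SAP 5.11.2 agrees with the protocol on rescue and goes beyond it on early stop.

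**Size of the effect on crude incidence.** The documents plan no hypoglycaemia figure, so there is none to reproduce. They give 145 patients per arm (123 completers / 0.85 = 144.7, rounded up) and 28 weeks of treatment. They give no hypoglycaemia incidence, and no stop or rescue rate by arm. The following are therefore assumptions: true incidence p is equal in both arms; the hazard is constant and unchanged after stopping; everyone who stops is followed to Week 28; a fraction s stops at Week 8; there is no rescue.

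- Hazard per week: λ = −ln(1 − p)/28.
- Counted incidence: (1 − s)·p + s·(1 − exp(−8λ)).
- For p = 0.40: λ = 0.5108/28 = 0.01824 and 1 − exp(−8λ) = 0.1358.
- s = 0.15: 0.85 × 0.40 + 0.15 × 0.1358 = 0.3604, or 36.0%.
- s = 0.05: 0.95 × 0.40 + 0.05 × 0.1358 = 0.3868, or 38.7%.
- Difference: −2.6 points, where the true difference is 0.

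| True incidence | Stops by arm | Counted incidence | Difference (points) |
|---|---|---|---|
| 20% | 10% vs 5% | 18.6% vs 19.3% | −0.7 |
| 40% | 15% vs 5% | 36.0% vs 38.7% | −2.6 |
| 60% | 20% vs 5% | 52.6% vs 58.2% | −5.5 |
| any | equal | equal | 0 |

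Timing matters too. For 15% versus 5% stops and true incidence of 20% to 50%, the gap is 1.0 to 2.2 points if stops are spread evenly over 28 weeks, and 1.7 to 4.1 points if all occur at Week 4.

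The formula does not depend on why follow-up is cut. Exchanging the two fractions, for example because one arm has more rescue, reverses the sign.

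**Time discarded** (stops at Week 8, so 20 weeks lost each): 145 × 0.15 × 20 = 435 patient-weeks versus 145 × 0.05 × 20 = 145, out of 145 × 28 = 4,060 per arm.

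**Rate model.** If the offset ends at the censoring date, events and time are cut together and the expected rate ratio is 1.00. If the offset keeps all 28 weeks, the ratio in the Week 8 example is (4,060 − 435)/(4,060 − 145) = 3,625/3,915 = 0.93. The corresponding values are 0.95 for evenly spread stops and 0.91 for stops at Week 4. The SAP does not say which offset applies.

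**The case against.** The strongest reply is that SAP 5.11.2 is a specific rule overriding a general one, chosen before unblinding, and that half of it (censoring after rescue) is the protocol's own. SAP 5.2 also allows the justification for a change to appear in the clinical study report, so its absence from the SAP is not yet a breach. This stands as far as it goes. It means that an all-data analysis would itself depart from the protocol after rescue. It does not account for the unqualified sentence in SAP 5.2, or for adding early stop to the protocol's rule.

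Four stronger readings are tempting and should not be drawn.

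- *That no uncensored hypoglycaemia information remains.* SAP 5.11.2 keeps a listing for all randomized patients, SAP 5.11.1 summarises hypoglycaemia as an event of special interest with no censoring stated, and protocol 9.2.2.1 has severe episodes reported as serious adverse events. What is missing is an uncensored between-arm comparison by level.
- *That dulaglutide, or the arm with more early stops, will look safer.* SAP 5.11.1 calls gastrointestinal events common on dulaglutide; it does not say that they lead to more stopping. More rescue on placebo would pull the other way.
- *That the rate analysis is biased.* That depends on an offset the SAP has not fully defined.
- *That residual drug exposure is cut off.* The protocol's four weeks concern reaching steady state. Neither document gives a washout, and SAP 5.11.2 does not define the cut date.

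The illustration is also modest against sampling error. At 40% incidence the standard error of the difference is √(2 × 0.4 × 0.6/145) = 5.8 points, more than twice the 2.6. In addition, Protocol 8.1.1 gives stoppers another glucose-lowering intervention, so their hazard may change, and patients who leave the study add no later data under either rule.

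**Conclusion.** The point holds as a contradiction in the text with a conditional consequence. SAP 5.11.2 conflicts with SAP 5.2 and exceeds protocol 10.3.4.3, with no reason recorded, and it sets aside collected safety data from the only comparisons by level. Crude incidence is distorted whenever early stops or rescue differ between arms in frequency or timing in a way that does not cancel. Under the assumptions shown, the size runs from 0 to about 5.5 points, with 2.6 points in the central example; the sign cannot be fixed from the documents. The rate comparison is sound if its offset is days at risk and otherwise off by roughly 5% to 9% in the 15% versus 5% examples. This should be corrected before analysis. It does not touch the primary HbA1c analysis.

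**What to change.** 1. Reconcile SAP 5.2, SAP 5.11.2 and protocol 10.3.4.3, and record the reason for the rule adopted.
2. Report incidence and rates of Level 1, 2, 3 and nocturnal hypoglycaemia on all collected ITT data, as SAP 5.2 requires. Keep the censored set beside it, labelled as on-treatment and pre-rescue.
3. State openly that the all-data set departs from the post-rescue censoring in protocol 10.3.4.3, and why.
4. Define the censoring date, and set the rate-model offset to log days at risk within each data set.
5. Treat off-drug time the same way for completers and early stoppers, and give the overall period one definition.
6. Reconcile Level 3 counts in the hypoglycaemia tables with the serious adverse event listing.

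The cost is SAP wording and one repeated set of tables from data already being collected. The downside is that the all-data set includes events on rescue or replacement agents; the censored set beside it lets the reader see how much they contribute.

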5.6. Primary Efficacy Analysis

The primary efficacy measurement in this study is change in HbA1c from baseline to Week 28, as determined by the central laboratory.

The primary analysis model will be MMRM for HbA1c change from baseline to Week 28 (Visit 17). The model will include treatment, OAM use, visit, treatment-by-visit interaction as fixed effects, and baseline HbA1c as a covariate and patient as a random effect. LS Mean, 95% CI and the p-value will be presented for the treatment difference (dulaglutide 1.5 mg minus placebo).

Primary analysis will be done using ITT population.

The MMRM analysis model for the primary endpoint will be repeated using the PP and Completer populations to check the sensitivity of the primary analysis.

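### Hypoglycaemia rate model: the offset is not cut where the events are cut, and the random effect and record unit are left unnamed

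*SAP*

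**What the plan says.** SAP 5.11.2 covers "The rates of hypoglycemic episodes (episodes/patient/year) for each visit, overall and maintenance period". These "will be analyzed using a generalized linear mixed-effects model assuming negative binomial distribution". The terms listed are treatment, OAM usage and baseline HbA1c stratum, all as fixed effects. No random effect, within-patient covariance or robust variance is named, and the section does not say what one record is. The offset is described as follows: "The logarithm of days between visits will be included as an offset to account for possible unequal duration between visits and between patients".

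Incidence and rates "will be reported for the ITT population without post-rescue or early-discontinuation data".

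The model in Protocol 10.3.4.3 used the same offset and also had visit, treatment-by-visit and baseline hypoglycaemia rate. It named no patient effect either. The SAP Revision History records this change: "Removed interaction term and covariate in negative binomial model for hypoglycemia events". The visit main effect has gone as well, while the visit-based offset stayed.

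Two further statements do not fit together:
- SAP 5.2 says that safety analyses do not censor data after rescue or early discontinuation; 5.11.2 excludes them.
- Within 5.11.2, the overall period is Weeks 0–28 in one paragraph, while overall incidence runs through safety follow-up in the next.

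**The concern.** There are two separate issues.

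**Numerator and denominator.** A rate needs events and time at risk cut at the same point. Protocol 5.1, 7.7.5.3 and 8.1.1 keep patients in the trial after rescue or permanent drug stop, so their visits continue. Days between visits then run past the date on which events stop being counted.

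**Clustering.** An offset in days between visits suggests several records per patient. If such records were pooled for the overall or maintenance period with only the listed terms, a patient's repeated intervals would count as independent and confidence intervals would be too narrow.

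Hypoglycaemia is an adverse event of special interest, and its comparison between arms is central when a drug is added to titrated insulin. A biased ratio or an over-narrow interval could be read as evidence of more, or less, hypoglycaemia.

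**Working it through.** The plan states no figure for this model. The arm size used below comes from SAP 5.1 and reproduces: 2 × (1.960 + 1.282)² × 1.2² / 0.5² gives 122 per arm by normal approximation (123 stated; power at 123 is 90.4%), and 123 / 0.85 gives 145 randomized per arm.

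**Visit intervals.** Office visits fall at Weeks 0, 1, 2, 4, 6, 8, 12, 18, 24 and 28. That gives nine intervals of 7, 7, 14, 14, 14, 28, 42, 42 and 28 days (196 in total), three of them in Weeks 12–28. Counting telephone visits gives 14 intervals.

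**Offset.** Assume a constant event rate, a share p of patients cut in an arm, and cut times uniform over 196 days.
- Mean time at risk is 196 × (1 − p/2).
- If the offset runs the full 28 weeks, the estimated rate is the true rate × (1 − p/2).
- If it runs only to the next visit, the mean excess per cut patient is ΣL²/(2 × 196) = 5782/392 = 14.75 days. The offset then averages 196(1 − p) + p × (98 + 14.75).

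Example with 15% cut on control and 2% on dulaglutide:
- Full 28 weeks: (1 − 0.01)/(1 − 0.075) = 0.990/0.925 = 1.070.
- To the next visit: (194.04/194.34)/(181.30/183.51) = 0.998/0.988 = 1.011.

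Rate ratio when the truth is 1 (cut shares assumed):

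| Cut share control / dulaglutide | Offset to next visit | Offset for full 28 weeks |
|---|---|---|
| 15% / 15% | 1.000 | 1.000 |
| 15% / 2% | 1.011 | 1.070 |
| 10% / 2% | 1.006 | 1.042 |
| 5% / 1% | 1.003 | 1.021 |
| 5% / 15% | 0.992 | 0.949 |
| 10% / 20% | 0.991 | 0.947 |

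Even with equal shares, the rates themselves are understated: at 15% cut, by 7.5% (full 28 weeks) or 1.2% (to next visit).

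**Clustering.** Trials were simulated with no treatment effect, 145 per arm, two-sided 5% (SAP 5.2), 1600 trials per scenario (Monte Carlo error about 0.5 points at 5%). Counts were Poisson with gamma multipliers of mean 1. The event rates (1 or 4 per patient-year), the between-patient variance (0 to 4) and the extra within-interval variance (0 to 1) are assumptions, since the documents give none. The model had treatment and the log-days offset.

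Type I error (%) for stacked interval records, no patient effect, model-based standard error, by between-patient variance:

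| Records per patient | Rate per year | 0 | 0.5 | 1 | 2 | 4 |
|---|---|---|---|---|---|---|
| 9 (office, Weeks 0–28) | 1 | 5.8 | 7.9 | 10.8 | 13.3–15.2 | 17.6 |
| 9 | 4 | 4.8 | 13.7 | 19.6 | 25.3–28.7 | 30.2 |
| 14 (with telephone) | 1 | 3.9 | 7.1 | 11.2 | 15.9–16.8 | 22.1 |
| 14 | 4 | 5.4 | 14.4 | 22.9 | 29.0–32.9 | 36.0 |
| 3 (maintenance) | 1 | 5.1 | 6.3 | 7.5 | 7.8–9.6 | 11.0 |
| 3 | 4 | 5.9 | 9.1 | 11.9 | 14.2–17.2 | 18.1 |

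With any between-patient variance, the mean model standard error was 0.48 to 0.96 of the true standard deviation. Hand check at nine intervals, rate 4, variance 2: 1.96 × 0.102/0.190 = 1.05, and a normal deviate exceeds that in absolute value about 29% of the time, against 28.7% simulated.

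On the same data, one record per patient gave 3.8% to 7.8%, and patient-clustered standard errors gave 3.8% to 6.8%. A random-intercept negative binomial model was not fitted; these two stand in for it.

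**The case against.** The strongest reply is that the clustering fault is not in the text. The SAP names a mixed-effects model, which implies a random part, and the phrase about fixed effects may describe only the fixed part. Asking for rates by visit, overall and for maintenance fits separate fits with one record per patient, and dropping the visit and interaction terms fits that too. It is true that SAP 5.6 spells out the patient term ("and baseline HbA1c as a covariate and patient as a random effect"), as do 5.7.2, 5.8.2, 5.11.4 and 5.12. But the repeated-measures models in 5.7.1 and 5.8.3 leave it out, so silence may be a drafting habit. All of this stands. A reader might infer that the plan treats repeated intervals as independent; the documents do not say so.

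A reader might also infer that the uncut offset shrinks standard errors. It does not: it understates rates, and it biases the ratio only when cuts differ between arms.

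On the offset itself, one can reply that excluding post-cut data implies excluding post-cut time. That may be the intention, but the offset is defined by visits and nothing ends it at the cut. If the general rule in 5.2 governed instead, events would be kept and the mismatch would vanish. However, the Revision History says that the analyses including those data were removed, which points to 5.11.2 as intended.

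Finally, hypoglycaemia is outside the graphical testing scheme (SAP 5.3), and the Fisher tests on incidence count patients, so within-patient clustering does not touch them. That limits the consequence.

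**Conclusion.** The offset point holds on the stated rules: an offset in days between visits, with events removed after rescue or drug stop, gives a rate that is too low. Its effect on the comparison is small. The ratio moves to 0.99–1.01 or 0.95–1.07, depending on how far the offset runs, for assumed cut shares of 1% to 20% that differ by arm, a constant event rate and uniform cut times. It does not move when shares are equal.

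The clustering point holds conditionally. It needs stacked interval records for the overall or maintenance period and no patient effect. Type I error is then about 6% to 36% for between-patient variance of 0.5 to 4, and about nominal at zero. A reader might conclude that false signals would be several times too frequent. That also needs marked heterogeneity (variance about 1 to 2 or more) with many intervals or a high event rate, none of which the documents give.

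What is certain is that the section allows readings with materially different error rates. It should be settled before unblinding.

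**What to change.** In SAP 5.11.2:
- For the overall and maintenance models, use one record per patient per period, with offset log(days from period start to the earlier of period end or the patient's censoring date).
- For by-visit rates, fit one record per patient for each visit, with the offset cut at the censoring date.
- If interval records are pooled instead, name a patient random intercept and cut the offset in the same way.
- State which rule applies to post-rescue and post-discontinuation data, and align 5.2 with 5.11.2.
- Give one definition of the overall period: Weeks 0–28 or through safety follow-up.

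The cost is SAP wording and a small programming change. No new data are needed, because the event exclusion already requires the censoring date.
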